**Controls:** For each case of JoRRP, up to 100 control subjects free of this diagnosis, at the time of the case’s diagnosis, will be identified from the cohort. As the number of controls per case increases beyond 4, improvement in statistical power diminishes [30]. However, given that data for additional controls are readily available in this database study, effort will be made to identify 100 controls per case. Cases and controls will be matched as closely as possible on age of mother (+/- 1 year), sex of child, and region where case was diagnosed. By design of the study (nested case-control), cases and controls will also be matched on calendar year of diagnosis. Controls will be selected from the population at risk at the point in time when a case is diagnosed with JoRRP. All controls who meet the matching criteria will be assigned a random number using SAS statistical software (SAS Institute Inc, Cary, NC) procedures. Then, 100 controls for each case will be selected at random from the pool of eligible controls. Controls will be assigned the same index date (date of birth) as the case to which they are matched. [Figure 1] provides an example of case/control subject selection nested within population-based cohort in this study.

**Exposure assessment:** The exposure of interest is GARDASIL or GARDASIL 9 vaccination in mother, one year prior to delivery, for each case and matched controls (see Figure 1 below).

PRODUCT: V501/V503	PROTOCOL/AMENDMENT VERSION NO.: V503-095-00-v3
REVOPS ID NO: NIS102781	CORE DRC APPROVAL DATE: 18MAR2024
EPIDEMIOLOGY NO.(PE STUDIES ONLY): 08039.022	

Exposure will be defined in 2 ways:

1. Exposure in primary objective: Fully vaccinated with GARDASIL/GARDASIL 9 (yes/no). A female/mother who received 3 doses (or 2 doses administered at 0 and 6-12 months if <15 years of age) of GARDASIL/GARDASIL 9 one year prior to delivery will be classified as exposed.
2. Exposure in sensitivity analysis: GARDASIL/GARDASIL 9 vaccination (yes/no). A female/mother who received at least one dose of GARDASIL/GARDASIL 9 one year prior to delivery will be classified as exposed.

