### 7.2.1 Inclusion Criteria

- Birth cohorts 2008 to 2020
- The study subject (child) must be born and resident in Sweden, Denmark or Norway as defined through the Total Population Registry for their entire life, to ensure incident JoRRP case is truly new onset.
- The study subject must be between 0 to 9 years of age (due to direct HPV-vaccine receipt at ages 10-12 years) through school-based programs in some countries.

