### 7.3.2 Outcomes

Health outcomes are defined as clinical events or outcomes which may be represented as diagnoses, treatment or procedures.

Definition of cases:

- A subject will be defined as having JoRRP if he/she has  $\geq 1$  hospitalization or outpatient record with diagnosis registered as D14.1, with appropriate topography/morphology codes (where possible to obtain from pathology/cancer registry), between 0-9 years of age [29].

Selection of controls: random selection of up to 100 controls per case from the underlying population at risk, using incidence density sampling procedures. Matching criteria will be age of mother (+/- 1 year), sex of child, calendar year of case diagnosis, and region where case was diagnosed.

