## 7.8 Data Analysis

### 7.8.1 Statistical Methods

Conditional logistic regression will be used for estimation of odds ratios (ORs) and corresponding 95% confidence intervals in the pooled analysis using 1-step approach, with adjustment for clustering and adjustment for relevant covariates; all measured with similar high accuracy in each country. Children whose mother received the bivalent vaccine, even in combination with GARDASIL or GARDASIL 9, will be excluded from the analysis. Similarly, in the primary analysis, children whose mother had history of genital warts prior to vaccination will be excluded as vaccination is exclusively prophylactic, i.e., there is no therapeutic effect against HPV infection or related disease.

Each case subject and his/her controls constitute a risk stratum, or a risk set matched on age of mother, sex of child, and region where case was diagnosed. The distribution of these factors is therefore equalized in the model by design, which removes the need for adjusting for these factors so long as the risk strata are retained. Regarding mode of delivery, history of maternal genital warts, maternal smoking status, education level and income, it was decided not to match on these factors, as they may be of interest to study as confounders or effect modifiers.

When the outcome of a study is rare, which is the case for JoRRP, the OR approximates the risk ratio (or relative risk, RR) [35]. Further, incidence density sampling (i.e. random sampling of controls from the available population still at-risk at the particular point in time of the case's diagnosis) also ensures that ORs are a direct estimate of the hazard ratio, again interpretable as the risk ratio in our study [36]. ORs obtained through the conditional logistic regression model will therefore be interpreted as the corresponding RR.

It is expected that use of ICD-10 code D14.1 will be highly accurate for diagnosis of RRP; however, where possible, effort will be made to further increase specificity, applying appropriate topography/morphology codes. We also plan to perform sensitivity analyses restricted to RRP cases with related diagnostic or other treatment procedures, and/or subcode D14.1.A, as described above.

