## Annex 2 TABLE AND FIGURE SHELLS FOR RRP STUDY (PRIMARY OBJECTIVE)

Table 2 Characteristics of Study Population, JoRRP Cases, and Control Subjects (prepared separately for each country)

	Study population, No. (%)	JoRRP cases, No. (%)	Controls, No. (%)
Age of child , years, mean (SD)			
Age of mother at delivery , years, mean (SD)			
Highest level of education achieved by mother*			
Low			
Medium			
High			
Missing			
Highest annual household family income level‡			
Low			
Medium			
High			
Missing			
Mother's country of birth			
Current country of residence			
Other country			
Missing			
Method of delivery			
Vaginal			
Cesarean			
Missing			
Maternal history of EGW			
Yes			
No			
Missing			
Maternal smoking status at first prenatal visit			
Yes			
No			
Missing			

EGW = external genital warts; JoRRP = juvenile-onset recurrent respiratory papillomatosis; SD = standard deviation

\*Education level of mother at index date.

‡Based on average level between 2006 (the start year of HPV vaccination) and the index date.

PRODUCT: V501/V503	PROTOCOL/AMENDMENT VERSION NO.: V503-095-00-v3
REVOPS ID NO: NIS102781	CORE DRC APPROVAL DATE: 18MAR2024
EPIDEMIOLOGY NO.(PE STUDIES ONLY): 08039.022	

Table 3 Number of Cases and Odds Ratio for Recurrent Respiratory Papillomatosis (RRP) by GARDASIL/GARDASIL 9 Vaccination Status, 2008-2020

GARDASIL/ GARDASIL 9 vaccination status	JoRRP (ICD-10 code: D14.1)			
	No. of cases 	No. of controls 	Crude OR (95% CI)	Adjusted OR  (95% CI)
Fully Vaccinated 			Ref.	Ref.
Unvaccinated				

*CI = confidence interval; HPV = human papillomavirus; ICD-10 = international classification of disease, 10th modification; JoRRP = juvenile-onset recurrent respiratory papillomatosis; OR = odds ratio; Ref. = reference.*

 All study participants who acquired a first diagnosis of D14.1 before age 10 years and appropriate topography/morphology code (if available from pathology/cancer registry).

 Up to 100 controls matched on age of mother, sex of subject, and region of diagnosis.

 Adjustment factors considered for inclusion include maternal education level, family income level, maternal smoking status, mother's country of birth, and method of delivery.

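### Controls are matched on the region of the case's diagnosis, an attribute that controls do not have; region of residence should be used for both, at one stated time point

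*Protocol*

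**What the plan says.** The matching rule appears in four places in the protocol, always tied to the case's diagnosis:

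- Section 7.1, Controls: "matched as closely as possible on age of mother (+/- 1 year), sex of child, and region where case was diagnosed".
- Section 7.3.2: the list of criteria ends with "calendar year of case diagnosis, and region where case was diagnosed".
- Section 7.8.1: each case and its controls form "a risk set matched on age of mother, sex of child, and region where case was diagnosed".
- Annex 2, Table 3, footnote 2: "Up to 100 controls matched on age of mother, sex of subject, and region of diagnosis".

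Section 7.8.1 then relies on the matching to balance these factors, "which removes the need for adjusting for these factors so long as the risk strata are retained". Region is not among the adjustment factors named in 7.8.2 or in Table 3 footnote 3.

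On the control side, 7.1 requires subjects without JoRRP at the time of the case's diagnosis and adds: "Controls will be selected from the population at risk at the point in time when a case is diagnosed with JoRRP". Residence enters the eligibility rules at country level only: the child "must be born and resident in Sweden, Denmark or Norway as defined through the Total Population Registry for their entire life". None of the registry lists in 7.4 names a region, whether of residence or of care.

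**The concern.** A matching factor has to be the same attribute in case and control. Here the case's value is defined by where it was diagnosed, and the control has no corresponding value. The obvious way to carry out the rule is to use the control's home region. That sets a place of care against a place of residence.

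The two agree for a case diagnosed in its home region. For a case that lives in region A and is diagnosed in region B, the controls are residents of B. Whether the mother was vaccinated depends on where she lived, not on where her child was later examined. If coverage differs between A and B, that difference enters the set's exposure contrast. Conditional logistic regression works within the set and cannot remove it, and no region covariate is planned. More controls per case do not help either, because they estimate coverage in the wrong region more precisely.

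**Working it through.** **Comparison of the passages.** All four statements use diagnosis and none uses residence, so this is not a slip in one sentence. The control attribute is undefined in each. This part needs no assumption about referral.

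**Possible size.** The protocol has no figure of its own on this point to reproduce. The following is an illustration.

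Inputs from the protocol (section 7.5): an OR of 3.0, unvaccinated versus fully vaccinated, and the coverage values 5% and 10%. Those values are the ends of the overall range used for power; treating them as a regional contrast is an assumption.

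Further assumptions: two regions, A and B, with half of the cases living in each; a share r of A's cases diagnosed in B and none of B's in A; controls drawn from residents of the diagnosis region; and enough controls that their exposure equals that region's coverage p.

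Probability that a case's mother is vaccinated, by home region X:

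π_X = o/(1 + o), with o = [p_X/(1 − p_X)]/3

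- p = 5%: o = 0.05263/3 = 0.01754, so π = 0.01724
- p = 10%: o = 0.11111/3 = 0.03704, so π = 0.03571

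Probability that the model assigns in a set whose controls come from X, with θ the odds ratio for vaccinated versus unvaccinated:

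P_X(θ) = p_X θ/(p_X θ + 1 − p_X)

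Score equation of the conditional likelihood:

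½(1 − r)[π_A − P_A(θ)] + ½r[π_A − P_B(θ)] + ½[π_B − P_B(θ)] = 0; the reported OR is 1/θ.

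Worked case, with A at 5%, B at 10% and r = 50%. The mean case exposure is ½(0.01724 + 0.03571) = 0.02648. At θ = 1/3.54, P_A = 0.01465 and P_B = 0.03043, and ¼ × 0.01465 + ¾ × 0.03043 = 0.02648. The equation balances, so the reported OR is 3.54.

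Expected OR when the true OR is 3.0:

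| Coverage A / B | r = 10% | r = 25% | r = 50% |
|---|---|---|---|
| 5% / 10% | 3.11 | 3.27 | 3.54 |
| 10% / 5% | 2.89 | 2.73 | 2.46 |
| 5% / 7% | 3.05 | 3.13 | 3.27 |
| 7% / 5% | 2.95 | 2.87 | 2.73 |
| 5% / 5% | 3.00 | 3.00 | 3.00 |

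With r = 0 every row gives 3.00. Because half of the cases live in A, r = 10% to 50% means that 5% to 25% of all cases are diagnosed away from home. With a true OR of 1.0 and the 5%/10% contrast, the result for r = 10% to 50% is 1.04 to 1.18, or 0.96 to 0.82 reversed.

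**After the change.** When case and control are matched on residence, each set compares π_X with P_X(θ) for the same X. The equation is solved by 1/θ = 3.0 for any r.

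**The case against.** A reader might infer that the odds ratio is biased and that controls come from a different source population. The documents support neither. Bias needs cross-region diagnosis and unequal regional coverage together, and the protocol reports no figure for either. Every control comes from the same national cohort and the same risk set in time; only one matching factor may be misaligned, and only in some sets.

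Referral itself is an inference from the rarity of the disease. Section 7.1 lists endoscopy and microlaryngoscopy codes for a sensitivity analysis, not as the route to diagnosis. The primary case definition in 7.3.2 needs only a hospital or outpatient record with the code, plus topography/morphology codes where obtainable. If region means a wide health-care catchment, much referral would stay inside it.

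The numerical scenario is also severe. It assumes up to a twofold coverage contrast and one-way movement; opposing flows would dilute it. The shifts are modest beside sampling error. With 200 cases, 20,000 controls and 5% coverage, about 200 × 0.01724 = 3.45 vaccinated cases are expected. The standard error of the log OR is then √(1/3.45 + 1/196.55 + 1/1,000 + 1/19,000) = 0.54. The largest shifts in the table are ln(3.54/3.0) = 0.17 and ln(2.46/3.0) = −0.20, or 0.3 to 0.4 standard errors. It would be tempting to add that the bias moves the estimate across the success threshold of 3.0. That says little, because a true OR of exactly 3.0 lies on the threshold and any shift crosses it.

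Finally, the wording could be meant as the case's home region at the time of diagnosis. Exact variable lists may also sit in the common data model and data orders described in 7.6, so the silence of 7.4 is weak evidence on its own.

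All of this limits the claim about size. It does not supply the missing definition. Footnote 2, with "matched on age of mother, sex of subject, and region of diagnosis", makes the residence reading less natural, and if residence was meant the protocol still has to say so.

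**Conclusion.** The point holds as a defect in the matching rule. Four places define region by an attribute that controls lack, and 7.8.1 relies on that rule to leave region out of the model. If place of diagnosis is compared with residence, region is not balanced in any set whose case was diagnosed away from home, and nothing later corrects it.

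Whether this distorts the result cannot be settled from the protocol. The bias is zero if either condition is absent, and its direction is unknown. Under the assumed 5% versus 10% contrast, with 10% to 50% of one region's cases diagnosed in the other, a true OR of 3.0 is estimated as 3.11 to 3.54 or 2.89 to 2.46. Under 5% versus 7% it is 3.05 to 3.27 or 2.95 to 2.73. Regional coverages and referral shares are assumptions throughout.

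**What to change.** In sections 7.1, 7.3.2, 7.8.1 and Table 3 footnote 2, replace region of diagnosis with region of residence, taken at the same stated time point for case and control. Two choices are defensible: the mother's residence at the child's birth, which is the index date set in 7.1, or residence at the case's diagnosis date, which fits the risk-set sampling. Neither is necessarily where the mother lived when vaccination was offered. What matters most is that case and control share one attribute and one date. Add region of residence to the registry data listed in 7.4.

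The cost is wording in four places and one registry variable. Controls need some region value to be matched at all, so no extra subjects are needed and the expected number of cases is unchanged. The change should be made before the risk sets are drawn.

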## 7 RESEARCH METHODS

### 7.1 Study Design

#### Nested case-control study (primary objective)

**Setting:** Sweden, Norway, and Denmark.

In 2006, the U.S. Food and Drug Administration and European Medicines Agency approved the use of GARDASIL. National HPV vaccination programs in Scandinavian countries (Denmark, Norway, and Sweden) were instituted in subsequent years (~2008 or afterward) for young female adolescents, with catch-up vaccination programs for cohorts of older adolescents, teens, and/or young women in Denmark and Sweden. In Denmark, GARDASIL

PRODUCT: V501/V503	PROTOCOL/AMENDMENT VERSION NO.: V503-095-00-v3
REVOPS ID NO: NIS102781	CORE DRC APPROVAL DATE: 18MAR2024
EPIDEMIOLOGY NO.(PE STUDIES ONLY): 08039.022	

was used from October 2008 to February 2016, Cervarix (recombinant HPV bivalent [types 16 and 18] vaccine) from February 2016 to November 2017, and GARDASIL 9 since November 2017 (currently in use). The national HPV vaccination program targeting girls aged 12 years (primary cohort) was introduced in 2009, with fully subsidized catch-up vaccination for girls 13-15 years of age available since 2008, and girls/women up to 27 years of age since 2012. In Sweden, national HPV vaccination program using GARDASIL was introduced in 2010, with large-scale vaccination and high coverage achieved in 2012, with GARDASIL 9 being used since 2020. Fully subsidized catch-up vaccination for girls aged 13-17 years has been available in Sweden since 2012, and partially subsidized for the same age group since 2007. In Norway, the HPV vaccination program was initiated in 2009, in which girls approximately 12 years of age were offered GARDASIL in a three-dose schedule (until 2017). Catch-up vaccination was offered in Norway during the period 2016–2019 to women born between 1991 and 1996. Since 2017, Cervarix has been used in Norway. In 2015, a 2-dose schedule (with doses administered at 0 and 6 months) was recommended for females  $\leq 14$  years of age in Denmark and Sweden.

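### Random selection of controls within ±1 year of maternal age leaves vaccine coverage unequal inside risk sets, so the 7.8.1 claim that no adjustment is needed fails and the primary OR is pulled slightly toward 1

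*Protocol*

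**What the plan says.** Section 7.1 (Controls) has cases and controls "matched as closely as possible on age of mother (+/- 1 year"), and on sex of child and region. It adds that "cases and controls will also be matched on calendar year of diagnosis". Section 7.3.2 repeats the same criteria. Within the caliper there is no preference for the nearest age: every qualifying child gets a random number and "100 controls for each case will be selected at random from the pool of eligible controls".

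Section 7.8.1 says of the matching factors, including maternal age: "The distribution of these factors is therefore equalized in the model by design, which removes the need for adjusting for these factors". No maternal age or birth-year term is named among the adjustment variables in 7.8.2 or in the Table 3 footnotes.

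Section 7.1 (Setting) shows that vaccine access follows age and cohort. For Denmark: "The national HPV vaccination program targeting girls aged 12 years (primary cohort) was introduced in 2009", with catch-up at ages 13–15 from 2008 and up to 27 from 2012. Sweden subsidised ages 13–17, partly from 2007 and fully from 2012. For Norway, besides routine vaccination at about age 12: "Catch-up vaccination was offered in Norway during the period 2016–2019 to women born between 1991 and 1996".

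Section 7.5 makes success depend on an estimated OR of at least 3.0 and a lower 95% bound of at least 1.33.

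**The concern.** Maternal birth year largely determines whether a mother was offered the vaccine before delivery. Subtracting ages from programme dates puts band edges at birth years 1985 (2012 − 27) and 1993 (2008 − 15) in Denmark, 1990 (2007 − 17) in Sweden, and 1997 (2009 − 12) for the routine programmes in Denmark and Norway.

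A case mother just outside a band is compared with some controls inside it, and a case mother just inside is compared with some outside. If the vaccine works, these two errors do not cancel. Conditional logistic regression assumes that the controls in a set have the exposure distribution of the case's own stratum. A caliper centred on the case breaks that assumption at every edge. With a success rule on the point estimate, even modest attenuation lowers the chance of success.

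**Working it through.** **The plan's own figure.** Section 7.5 states 94% power for 200 cases, 100 controls per case, 5% coverage and OR 3.0, with lower bound above 1.33. Case exposure is p1 = 3×0.05/(0.95 + 0.15) = 0.1364. At OR 1.33 it is 0.0665/1.0165 = 0.0654. The difference is 0.0709. The standard error at OR 1.33 is √(0.0654×0.9346/200 + 0.05×0.95/20,000) = 0.0176. At p1 it is √(0.1364×0.8636/200 + 0.05×0.95/20,000) = 0.0243. So z = (0.0709 − 1.96×0.0176)/0.0243 ≈ 1.50, and power ≈ 0.933. The figure reproduces, with OR 3.0 taken as a raised odds of vaccination in cases. It uses one coverage value throughout, so it makes no allowance for imbalance within sets.

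**Estimating equation.** Let N_b be births to mothers born in year b, p_b the coverage in that year, and q_b the births-weighted coverage over b−1 to b+1. Let t0 = 1/3 be the true odds ratio for vaccinated versus unvaccinated. The large-sample conditional logistic estimate t solves

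Σ N_b p_b t0 = Σ N_b (1 − p_b + p_b t0) · q_b t / (1 − q_b + q_b t).

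Table 3 takes fully vaccinated mothers as the reference, so the reported OR is 1/t. With exact birth-year matching q_b = p_b, and t = t0 solves it.

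**A case checkable by hand.** Take four consecutive birth years inside a longer run, with equal births and coverage 0, 0, 80%, 80%. Then q = 0, 0.267, 0.533, 0.8. True exposed cases, per unit of births, are 0, 0, 0.267, 0.267 (sum 0.533). At t = 1/3 the model expects:
- year 2: 0.0889/0.8222 = 0.108
- year 3: 0.4667×0.1778/0.6444 = 0.129
- year 4: 0.267

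The sum is 0.504, below 0.533. The shortfall in year 3 (0.138) exceeds the excess in year 2 (0.108), so t must rise. At t = 0.367 the terms are 0.118 + 0.138 + 0.278 = 0.533, giving OR = 1/0.367 = 2.72.

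**Fuller scenarios.** Assumptions not in the documents: maternal age at delivery normal with mean 30.5 and SD 5; births 2008–2020; the coverage curves; constant baseline risk unless stated. True OR is 3.0.

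| Coverage by maternal birth year | OR with ±1 year |
|---|---|
| Step at 1993, 0% to 80% | 2.65 |
| Step at 1993, 2% to 80% | 2.78 |
| Step at 1993, 2% to 70% | 2.84 |
| Norway-like, two steps | 2.88 |
| Smooth rise centred on 1993 | 2.90 |
| Sweden-like, three steps | 2.92 |
| Denmark-like (about 22% overall) | 2.94 |
| Step at 1993, 2% to 30% | 2.95 |
| Single steps calibrated to 5% overall | 2.75–2.99 |
| Single steps calibrated to 10% overall | 2.77–2.96 |
| Exact birth year, every curve | 3.00 |

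These figures move by up to about 0.04 with how births are binned. Giving half weight to the outer years (exact ages rather than whole years) gives 2.64–2.95. A baseline-risk trend of −5% to +10% per maternal birth year gives about 2.64–2.96.

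**Set against sampling error.** In the protective direction, expected exposed cases are 200×0.0333/0.9333 = 7.1 at 10% coverage and 200×0.0167/0.9667 = 3.4 at 5%. The log-OR standard error is then roughly 1/√7.1 = 0.37 to 1/√3.4 = 0.54. The bias on that scale is ln(3/2.99) = 0.003 to ln(3/2.65) = 0.124.

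Simulated studies of 200 cases with 100 controls each, exact matching versus ±1 year:

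| Curve | Median OR | P(OR ≥ 3) | P(lower bound > 1.33) |
|---|---|---|---|
| Step at 1993, 2% to 80% | 3.01 vs 2.81 | 0.50 vs 0.45 | 0.24 vs 0.22 |
| Sweden-like | 3.11 vs 2.99 | 0.53 vs 0.50 | 0.41 vs 0.38 |
| Smooth | 3.13 vs 2.97 | 0.54 vs 0.49 | 0.39 vs 0.34 |

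These probabilities lie far below 94% because so few cases are exposed when the effect is protective. That is a separate matter from the caliper.

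**Would a model term repair it?** Keep the ±1 sets and add γ_b for maternal birth year. If every birth year has its own γ, the γ score equations force fitted cases in each birth year to equal actual cases. The exposure score is then solved by t = t0. Solving numerically for three of the 1993 steps (0% to 80%, 2% to 80%, 2% to 30%) returned 3.00 with a categorical term. A linear term left the estimates unchanged to within 0.01.

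**The case against.** The strongest reply is that the size rests on assumed curves. The protocol gives no coverage by birth year, only 5–10% overall. This stands: no single figure can be derived from the documents. A reader might infer that eligibility is set by single birth years and that 3.0 becomes a definite 2.7–2.9. Section 7.1 does not support that. Catch-up ran in multi-year bands, 7.4 adds vaccination outside the programmes, and coverage may rise gradually. The Norwegian 1991–1996 band is weak evidence of a sharp edge, because that catch-up ran in 2016–2019, Cervarix was in use there from 2017, and children of Cervarix recipients are excluded.

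Second, the bias is conservative and small beside the sampling error. This also stands. An unmatched approximation at 10% coverage puts the chance of meeting both success conditions at about 58% for OR 3.0 and 46–54% for 2.7–2.9. At 5% coverage it is about 11–14% against 8–13%. In two of the three simulated curves the ±1 median was nearer 3.0 than the exact-match median, because small-sample bias away from the null offset the caliper. That is two errors cancelling, not support for the caliper.

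Third, the opening phrase of the matching rule could make ±1 year an outer limit, and 7.11 leaves the covariate set open. The random-draw sentence defeats the first reading. On the second, 7.8.1 says that maternal age needs no term.

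Fourth, exact birth year is not a complete cure. Exposure also depends on delivery date, and the child's birth year is not a listed matching factor. This is correct and shapes the fix.

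**Conclusion.** The concern holds in limited form. Section 7.8.1 claims for a ±1 year caliper what only exact matching, or an adequate model term, delivers. Every curve tried gave attenuation. Given the assumed maternal age distribution and coverage curves, a true OR of 3.0 is estimated at about 2.65–2.99, lowest for a sharp high-contrast step and close to 3.0 for a shallow one. This does not threaten the validity of the study or create a false claim of effectiveness. It deserves correction because the success rule in 7.5 acts on the point estimate and the repair is cheap.

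A reader might also infer a much larger bias from the missing reference date for maternal age. If age were taken at each child's own delivery, mothers' birth years could differ by several years, and a half-width of 3–5 years gives 2.1–2.6 on the two curves tried. The documents do not establish this. Controls take the case's date of birth as index date, which is compatible with measuring maternal age at one common date. The date simply needs to be stated.

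**What to change.** 1. In 7.1 and 7.3.2, match on the mother's calendar year of birth. Allow ±1 year only where too few same-year controls exist, with the threshold stated.
2. Add maternal birth year to the conditional logistic model as a categorical or flexible term. A linear term would not capture a step. If sets have already been drawn with the caliper, the categorical term alone repairs the estimate in the model above.
3. State the date at which maternal age is taken, and whether in whole years or exact dates. State how differences in delivery date within a set are handled, since exposure must precede delivery by a year.
4. In 7.8.1, limit the no-adjustment statement to factors matched exactly.

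The cost is one sampling parameter, one model term and some wording, on registry data already requested. Some sets in small regions will have fewer than 100 controls. The protocol's Table 1 shows how little that matters: at 200 cases, OR 3 and 5% coverage, power is 0.94 with 100 controls per case and 0.92 with 10.
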